11.1. INSTITUTIONAL REVIEW BOARD (IRB) REVIEW	
11.2. CONSENTING PROCEDURE , INFORMED CONSENT FORMS, AND STUDY INFORMANTS	18
11.3. Participant Confidentiality	19
11.4. Participant Compensation	19
11.5. Study Discontinuation	20
12. PUBLICATION OF RESEARCH FINDINGS	20
13. REFERENCES	21

STUDY TEAM ROSTER

[name], MS (Principal Investigator)

Section of Geriatrics and Gerontology

[name], PhD (Co-investigator, Neurologist)

Department of Neurology

Department of Medicine

[name] (Co-investigator, MRI expert)

Division of Magnetic Resonance Research

Department of Radiology

[name] (Co-investigator, Neuropsychologist)

Department of Neurology

[name] (co-investigator, Medical Physicist) Department of Radiology

Department of Radiology

[name] (Co-investigator; Statistician)

Department of Biostatistics and Bioinformatics, Rollins School of Public Health, Emory University,

[name] (Co-investigator, Neuroproteomics)

Director, Emory NINDS-Neuroscience Proteomics Core Facility

PARTICIPATING STUDY SITES

Wesley Woods Health Center

Emory University Hospital Clinical Research Network

Executive Park Medical Campus

PRÉCIS

Study Title

Candesartan's Effects on Alzheimer's Disease And Related Biomarkers

Acronym

CEDAR

Objectives

Our *Primary objective* is to determine the safety and dose-response for target engagement of the treatment with escalating doses of candesartan in those with mild cognitive impairment (MCI) and Alzheimer's disease (AD) based on cerebrospinal fluid levels of amyloid and tau.

Our *secondary objectives* are to assess the efficacy of 1 year treatment of candesartan on biomarkers of vascular function, neurodegeneration, and neuro-inflammation; to assess the efficacy of 1 year treatment with candesartan on amyloid imaging; and to estimate the effect size of candesartan on cognitive and functional measures in MCI and AD.

Design and Outcomes

This is a double-blind placebo-control randomized clinical trial that compares candesartan to placebo in individuals with MCI who also have positive AD biomarkers. Our measures include cognitive function, cerebral perfusion and reserve, markers of vascular brain damage, atherosclerosis, arterial stiffness, vascular inflammation and endothelial function. Amyloid and Tau PET imaging will be collected on a subgroup of this trial.

Interventions and Duration

The intervention includes candesartan (8, 16, or 32 mg) or placebo. The duration of the study is 1 year.

Sample Size and Population

Our target population includes subjects who are 50 years or older who are not receiving antihypertensive medications with MCI and AD. Our sample size is 72 for this trial. All 72 subjects will be invited to participate in the additional PET study.

SCHEDULE OF PROCEDURES FOR THE DURTAION OF THE STUDY

Phase:	SCREEN	BASELINE		TITRATION		FOL	LOW	-UP
Number of visits	1-2	1-3		2			4	
Months	-1	0		1-2	3	6	9	12
Informed Consent	Х							
Cognitive screening	Х							
Screening labs	X*							
Amyloid Positivity to assess eligibility	X**							
CSF for molecular analysis	X***	X***						Х
Weight/Height		Х		Х	Х	Х	Х	Х
Blood Pressure	Х	Х	NOI	Х	Х	Х	Х	Х
Safety labs			IZAT	X#	X#	Χ^	X#	Χ^
Brain MRI		Х	MO					Х
In-vivo A β and Tau PET scan	X**	X**	AND					Х
Vascular function measures		Х	R					Х
Cognitive Battery		Х				Х		Х
Functional battery (IADL, SPPB)		Х						Х
RAS biomarkers (blood and CSF)		Х				Х		Х
APOE genotype		Х						
Retinal scan and blood draw****								
Inflammatory/molecular biomarkers (proteomics /metabolomics)	X\$	X\$						X
Time (in minutes)	60-120	150-210		30	30	75	30	150-210

*: Screening labs include: CBC, CMP (BUN, CR, electrolytes, liver function), B12, TSH and PT/INR

**: Amyloid positivity can be assessed by either LP (CSF levels of amyloid) or PIB-PET. We will routinely use LP as the default method to determine Amyloid positivity however, in some instances e.g. a failed LP or delayed CSF results due to lab issues then we will use a screening PIB-PET instead. If a PIB-PET was done at screening, it WILL NOT be repeated at baseline. Subjects will only have Tau-Pet at baseline.

***: If subject has had an LP within the 6 months prior to their screening/baseline visit and samples are available for assessing eligibility and for measuring CSF outcomes then no LP will be done at screening. If CSF is only available for eligibility assessment (e.g. from PIB-PET/ clinical LP/assessment/ another research study and subject willing to share these samples) then an LP will be done to obtain CSF for the outcome measures (such as molecular analysis). This LP can be done at baseline instead of screening (since eligibility would have been already established).

****: Retinal scan +/- 10 cc blood draw are optional and can be done at any visit or after the completion of the study.

#: Safety labs at titration, 3 and 9 months include BMP (BUN, CR, electrolytes)

^: Safety labs at 6 months and 12 months include BMP (BUN, CR, electrolytes) + CBC. If subject started taking any blood thinners during the study, PT/INR will be repeated before LP at 12 months.

\$: Samples for inflammatory/molecular biomarkers will be drawn either at screening or at baseline visits.

1. STUDY OBJECTIVES

Our *Primary objective* is to determine the safety and dose-response of target engagement for treatment with escalating doses of candesartan in those with mild cognitive impairment (MCI) and Alzheimer's disease (AD).

Our *secondary objectives* are to assess the efficacy of 1 year treatment of candesartan on biomarkers of vascular function, neurodegeneration, and neuro-inflammation; to assess the efficacy of 1 year treatment with candesartan on amyloid imaging; and to estimate the effect size of Candesartan on cognitive and functional measures in MCI and AD.

2. BACKGROUND AND RATIONALE

Available treatments for AD do not address novel neurovascular and inflammatory pathways. Prior research has documented that the antihypertensive angiotensin receptor blockers (ARBs), in general, and candesartan, in particular, may have a positive effect on both AD biomarkers and clinical manifestations.

2.1. DISEASE TARGETS FOR ARBS IN AD

AD is a multifactorial and a multisystem disease. ARBs target vascular, inflammatory, and amyloid pathways involved in AD initiation or progression shown in **Figure 1**. At the neurovascular level, ARBs improve cerebral perfusion and restore neurovascular coupling and microvascular function.¹⁻³ Both MCI and AD individuals exhibit significant microvascular dysfunction as reflected by declines in vasodilator response to CO2 (Vasoreactivity).⁴ Our work suggests that in MCI, RAS activation leads to lower vasoreactivity, and ARBs may improve this measure which translates into improved cognition.^{1,5} Peripheral vascular markers including increased arterial stiffness

(which correlates with amyloid deposition in the brain^{6,7}) and decreased microvascular regeneration capacity reflected by circulating endothelial-related progenitor cells (EPC)⁸ are both observed in AD. EPC's have a potential role in repairing the blood brain barrier (BBB) endothelium^{9,10} by differentiating into BBB like-cells^{11,12} and improving neurovascular healing.¹³ EPC are decreased in AD patients ⁸ and correlate positively with cognitive function.⁸ Ang II (via AT1) leads to smooth muscle hypertrophy¹⁴ and inflammatory release of endothelial-related mediators, 15 resulting in increased stiffness. 16 AB 17 and Ang II¹⁸ reduce EPC counts and function leading to apoptosis, and ARBs may inhibit these effects in animal models.¹⁹ ARBs also inhibit AB induced neurovascular

impairments, independently of BP.²⁰⁻²² Aβ is transported back from the blood to the brain by receptors for advanced glycation end products (RAGE) on the endothelium.²³ Ang II up-regulates RAGE and increases BBB permeability by increasing oxidative stress²⁴ and disrupting tight junctions.^{25,26} ARBs inhibit the expression of RAGE²⁷ and restore BBB integrity by "healing" its endothelium. Ang II also increases and ARBs inhibit glycogen synthase kinase 3β (GSK3β) activity.²⁸ GSK3β increases tau phosphorylation and synaptic defects and is initiated in the earliest stages of clinical AD.²⁹⁻³¹ ARBs hence may decrease p-tau levels as suggested by a recent rat experiment. ³² This multi-target characteristic of ARBs increases the likelihood of producing a disease-modifying effect, rather than a symptomatic effect as provided by currently approved medications.

2.2. SAFETY OF ARBS IN NON-HYPERTENSIVE INDIVIDUALS

Prior studies in non-hypertensive individuals with normal cognition have shown that it has a good safety profile

with respect to adverse events and hypotension. In a non-hypertensive sample, Losartan (at equipotent candesartan doses; n=142 nonhypertension) had similar BP declines (4.7/3 mm Hg) compared to placebo.³³ (**Table-1**) In the Diabetic Retinopathy

Table 1: Pre-and post-treatment blood pressures in 142 non- hypertensive individuals			
	Week 0	Week5 (50 mg)	Week10 (100 mg)
Losartan	135.9/78.8	132.4/76.8	131.3/75.8
Placebo	138.3/80.3	136.1/79.7	138.4/80.7

Candesartan Trial Program [n=3,326, follow-up=5 years, pretreatment BP: 115-118/70-75 mm Hg], systolic blood pressure (SBP) reductions were in the range of 2.6-3.6 mm Hg in the candesartan arm and 2.5-2.7 in the placebo arm with no diastolic blood pressure (DBP) changes. ³⁴ These declines were not associated with hypotensive symptoms.

2.3. STUDY RATIONALE

In the brain, Angiotensin II (Ang II) binds AT1 and AT2 receptors. AT1 activation increases oxidative stress,³⁵ endothelial dysfunction, vasoconstriction and hypoperfusion, cholinergic depletion, neuro-degeneration, and memory loss.³⁶⁻³⁹ AT2 improves endothelial function, increases cerebral perfusion,⁴⁰ decreases superoxide production,⁴⁰ promotes neuronal cell differentiation,⁴¹⁻⁴⁸ and facilitates memory functions.^{49,50} Blocking the effect of Ang II, a crucial mediator of neuro-vascular injury, using ARBs may address shortcomings of current treatments. ARBs affect multiple systems involved in AD: vascular function, blood pressure (BP), inflammation, and the amyloid cycle.[see review⁵¹]

3. STUDY DESIGN

This is a **PHASE II** 1-year double-blind placebo-controlled randomized clinical trial where participants will be treated with candesartan (escalating doses: 8, 16 to 32 mg) or matched placebo.

4. SELECTION AND ENROLLMENT OF PARTICIPANTS

4.1. INCLUSION CRITERIA

(1) Age: 50 years or older;

(2) MCI will be defined as:

(i) Subjective memory concern;

(ii) Abnormal memory function documented using the Logical Memory subscale (Delayed Paragraph Recall, Paragraph A only) from the Wechsler Memory Scale-Revised (the maximum score is 25): [<11 for 16 or more years of education; <9 for 8-15 years of education; <6 for <7 years of education];

(iii) Montreal Cognitive Assessment (MoCA) < 26;

(iv) Clinical Dementia Rating scale /Memory sum Box score=0.5.

(v) General functional performance sufficiently preserved (Functional Assessment Questionnaire<9);

(3) Amyloid positivity: This will be determined by measuring the amyloid content in the brain. This can be determined by either CSF amyloid level or an amyloid scan (PIB-PET). We will plan to use CSF levels of amyloid as our default method. However, if we are not able to determine eligibility using CSF levels then a PIB-Pet will be performed to assess amyloid positivity.

In instances where the diagnosis of MCI is not clear, a review of the subject cognitive and non-cognitive data will be performed by the study physicians or neuropsychologists and a diagnosis of MCI will be based on the clinical judgment of the study physicians or neuropsychologists.

4.2. EXCLUSION CRITERIA

(1) Intolerance to ARBs;

(2) Current use of ARBs or ACEI (use of antihypertensive medications other than ACEI or ARBs for other indications is allowed);

(3) Current diagnosis of hypertension or current use of antihypertensive medication that is prescribed specifically for hypertensive therapy;

(4) SBP less than 110 or DBP less than 40 mm Hg;

(5) Renal disease (Creatinine >2.0 mg/dl), hyperkalemia (K>5.5 meq/dl), platelets<50,000/μl, or INR>1.9;

(6) Active medical or psychiatric diseases that in the judgment of the investigator would affect the safety of the subject or scientific integrity of the study e.g. if the patient has hypothyroidism or low vitamin B12 that is contributing to the subject's cognitive impairment;

(7) Uncontrolled congestive heart failure reflected by poor exercise tolerance and shortness of breath;

(8) History of stroke in the past 3 years;

(9) Inability to have MRI (eg metal implants or cardiac pacemaker) with an exception for those who cannot have an MRI, if all other parts of the study are obtained successfully they may still be enrolled in the study, or cognitive assessment or inability to assess amyloid positivity (no LP and no amyloid scan);

(10) History of increased intracranial pressure (ICP) or bleeding diathesis (from disease states or from use of anticoagulants such as warfarin, heparin and related products, Rivaroxaban or Xarelto, Apixaban or Eliquis, Edoxaban or Savaysa, Dabigatraban or Pradaxa);

(11) Women of childbearing potential (non-menopausal);

(12) In those who are unable to demonstrate that they understood the details of the study (ie lack of decisionalcapacity to consent), a study partner/surrogate who can sign on their behalf will be required, otherwise they will be excluded;

(13) Current use of Lithium, as Candesartan may increase lithium concentration to toxic levels.

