7. SAFETY ASSESSMENTS

7.1. SPECIFICATION OF SAFETY PARAMETERS

(i) The following safety parameters are related to the use of Candesartan: rash, dizziness, cough, weakness, fatigue, headaches, lower extremity edema, constipation, back pain, sore throat, upper respiratory tract infection, rhinitis, pharyngitis and hoarseness. Angioedema, renal failure (Cr>2.5), hyperkalemia (K>5.9 meq/dl), and fainting are also potential complications of candesartan.

(ii) The following safety parameters are related to the conduct of the study procedures: Neuropsychological assessment may be accompanied by anxiety, frustration and overall fatigue. The attachment and removal of a blood pressure cuff, cuffs for venous occlusion, and ultrasound probe on the neck may cause mild discomfort. Brain imaging requires the participant to stay still and lie down for 50-70 minutes, which may cause boredom and minimal reversible back pain. Because of the closed space and noise, undergoing an MRI may be associated with anxiety or panic reactions. We will ask participants to breathe via a mask air richer in CO2 than normal atmospheric air (5-8%) during the brain MRI procedure. The reported potential side effects may include a feeling of dizziness, faintness, or anxiety during CO2 inhalation. CO2 administration will be promptly terminated if any of the aforementioned conditions occur. The vascular ultrasound is safe and only mildly uncomfortable due to

tightness in the arm when the cuff is inflated. We will use ultrasound to painlessly bounce sound beams off of the carotid artery using a pencil-like sensor.

(iii) The following safety parameters are related to the LP procedure: The most common complication of a lumbar puncture is post-LP headache. We use a smaller 24-gauge Sprotte spinal needle. All subjects will be counseled on the signs and symptoms of post-LP headaches and given information on management (acetaminophen, caffeine, rest). Bacterial meningitis and a CSF leak are very rare complications of lumbar punctures. A blood patch is rarely needed to heal CSF leaks. All subjects will be instructed to promptly contact us if the headache persists beyond 3 days and if a blood patch is required, the cost of the patch will be covered by the funds supporting this project.

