8. INTERVENTION DISCONTINUATION

A subject may choose to withdraw from the study for any reason. The investigators may also request that the subject withdraw from the study, for safety or other reasons. The criteria for discontinuing a subject's participation include:

(1) the subject's request,

(2) adverse events that requires un-blinding or necessitate stopping the study drugs,

(3) persistent (>2 episodes on 2 separate days) of symptomatic hypotension or a blood pressure <100/40 mm Hg on 2 separate occasions despite adjusting study medication to the lowest dose (see section on follow-up on AE 7.4).(4) new clinically evident stroke or myocardial infarction or other event that limits ability to complete the study procedures

(4) inability to participate due to relocation or other personal reasons,

(5) renal failure (increase in serum Creatinine above 2.5 mg/dl) or hyperkalemia (greater than 5.9 meq)

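### The potassium limits carry a wrong or incomplete unit in all four places where they are used: three are per decilitre and one has no volume

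*Combined protocol and SAP*

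**What the plan says.** Four places in the combined protocol and SAP set a potassium limit.

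- Section 4.2, exclusion criterion (5): "hyperkalemia (K>5.5 meq/dl".
- Section 7.1, item (i), among the potential complications of candesartan: "hyperkalemia (K>5.9 meq/dl".
- Section 8, the last discontinuation criterion: "hyperkalemia (greater than 5.9 meq", with no volume after the unit.
- Section 9.3, Table 2, safety outcome row: potassium above 5.9, again in milliequivalents per decilitre.

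The creatinine limit beside potassium in section 4.2 reads "Renal disease (Creatinine >2.0 mg/dl". Section 8 and Table 2 also give creatinine in mg/dl.

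On-study potassium comes from the safety laboratory panels. The footnote to the schedule of procedures says "Safety labs at titration, 3 and 9 months include BMP (BUN, CR, electrolytes", and the 6- and 12-month panels include the same chemistry. Neither the schedule nor section 6.9 states the unit in which the laboratory reports potassium. No section gives a potassium limit per litre or corrects the unit.

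**The concern.** These entries decide who may enter (4.2), who stops (8) and what is counted as a safety outcome (Table 2). Safety is part of the primary objective in the Précis and in section 1, and section 7.1 names hyperkalaemia as a potential complication of the study drug.

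A limit given per decilitre is ten times as high as the same number per litre, and a limit in milliequivalents alone is an amount, not a concentration. If the printed unit were carried into an eligibility check, a database edit check or the code for the Table 2 outcome, the limit would not do its job. The reader cannot settle the intended unit from the documents.

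**Working it through.** The plan contains no calculation to reproduce. The check is a unit conversion and a side-by-side reading.

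**Inputs from the documents:** 5.5 meq/dl (4.2), 5.9 meq/dl (7.1), 5.9 meq without a volume (8), 5.9 mEq/dl (Table 2).

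**Assumption, not in the documents:** serum potassium in this population lies between 3.5 and 12 meq/L. The range is deliberately generous at the top.

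**Step 1, conversion.** 1 L = 10 dl, so limit per litre = limit per decilitre × 10.
- Entry: 5.5 × 10 = 55 meq/L.
- Safety parameter and Table 2 outcome: 5.9 × 10 = 59 meq/L.

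**Step 2, can the literal limits be met?** The assumed range in the printed unit is 3.5 / 10 = 0.35 to 12 / 10 = 1.2 meq/dl. No value in it exceeds 5.5 or 5.9 meq/dl. At the top of the range the shortfall is 55 / 12 = 4.6-fold for the entry limit and 59 / 12 = 4.9-fold for the on-study limit.

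**Step 3, the discontinuation limit.** Section 8 gives no volume, so the tenfold conversion cannot be applied. The entry is undefined as written.

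**Step 4, effect of the unit alone.** Read per litre, the same printed numbers fall inside the assumed range. A value of 6.5 meq/L, for example, exceeds both 5.5 and 5.9, whereas the same value as 0.65 meq/dl exceeds neither per-decilitre limit. This shows only what the unit does; it does not establish which limit is clinically right.

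**Step 5, do the numbers agree?**

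| Place | Purpose | Number | Unit printed |
|---|---|---|---|
| 4.2 (5) | Entry | 5.5 | meq/dl |
| 7.1 (i) | Safety parameter | 5.9 | meq/dl |
| 8 | Discontinuation | 5.9 | meq |
| Table 2 | Safety outcome | 5.9 | mEq/dl |

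The three on-study entries share one number. The entry limit differs from them, but it serves another purpose, and creatinine follows the same pattern: 2.0 at entry, 2.5 on study. The discrepancy is in the unit, not in the number.

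**The case against.** The best defence is that nobody would apply these limits literally. Each of the first three entries names hyperkalaemia and gives the number beside it. The values come from routine chemistry panels, and clinical staff would compare the printed number with the laboratory's result. The per-decilitre unit was plausibly carried over from the adjacent creatinine limit, although that is an inference. Other provisions also act. Section 4.2 (6) lets the investigator exclude for active disease that affects safety, section 8 allows withdrawal for safety and for adverse events that require stopping the drug, and Table 2 separately counts adverse events, serious adverse events and discontinuations. A clinically important rise in potassium could therefore still be acted on and recorded.

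This stands as a reason for low severity. It does not make the printed units right, and it relies on staff correcting the document silently.

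A reader might also draw three stronger conclusions, which the documents do not support:

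- **That the stopping rule can never act.** Section 8 has no decilitre in it. The limit there is incomplete, not out of reach.
- **That the thresholds contradict one another.** The on-study number is 5.9 throughout, and 5.5 belongs to entry.
- **That the hyperkalaemia outcome will be zero in both arms, or that programmed checks will carry the error.** Either would follow only if the printed unit were applied literally. Section 10.2 mentions range and logic checks in general terms and specifies no unit field or check definition.

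**Conclusion.** The point holds as a unit error of low severity. The per-decilitre entries in 4.2, 7.1 and Table 2 are wrong as written: they equal 55 and 59 meq/L, which lie 4.6 and 4.9 times above even the top of the assumed potassium range. Taken literally, the exclusion and the Table 2 outcome could not be met. The section 8 entry lacks a volume and so defines no concentration.

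The conversion is exact. The statement that the limits cannot be met rests on the assumed range of 3.5 to 12 meq/L, but the margin is wide enough that the exact upper end matters little. The practical effect is probably small, because staff are likely to use the laboratory's unit. The error matters most in Table 2, where the limit defines a countable safety outcome. No sample size, power, alpha or effect estimate is affected.

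**What to change.** Reconcile the four entries. State potassium in the unit in which the study laboratory reports it, written identically in sections 4.2, 7.1 and 8 and in Table 2, and have the investigators confirm the intended entry and on-study limits in that unit. No clinical threshold is proposed here. Any eligibility form, edit check or outcome code that already carries the printed unit should be checked against the corrected text.

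The cost is the correction of four entries in a protocol amendment, plus that check. The design and the analysis methods do not change.

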4.3. STUDY RECRUITMENT

Potential participants will be identified through community activities, health fairs, and patient referrals. Below we describe our recruitment venues:

(1) The Emory Alzheimer's Disease Research Center (ADRC) Clinical Core registry of research participants will be utilized for recruitment. Participants have agreed to be referred to other studies.

(2) Community-based recruitment: Community education sessions in local neighborhoods e.g. churches or barbershops will be conducted and attendees will be invited to participate in this study.

(3) MindMate App recruitment: MindMate users have the opportunity to first express their interest in clinical studies within the 'Research' section of the app. MindMate can also reach out to users once they have consistently utilized the app, usually after 3-4 weeks, & ask the user if they would like to receive further

information when a matching clinical study is available in their area. All users that are interested in participating in a clinical study must then go through a multi-stage opt-in & consent process. After MindMate matches a user to an open clinical trial, they automatically ask if they're happy to be contacted by a researcher to learn more about an open study they might qualify for.

(4) Physician recruitment: Local physicians (primary care or specialty physicians) will be informed of the study and its criteria and provided information about referral to the study personnel. In addition, flyers for the study will be posted at outpatient areas in the local medical facilities.

